13.6.5 Electrocardiogram (ECG)

Absolute values and change from baseline for heart rate, PR interval, QRS duration, QT interval, QT interval corrected for heart rate based on Bazett's formula (QTcB), and QT interval corrected for heart rate based on Fridericia's formula (QTcF) will be tabulated by period and visit.

The number and percentage of subjects for each category of ECG evaluation (abnormal clinically significant, abnormal not clinically significant, normal and unevaluable) will be presented by visit for each period.

In addition, the number and percentage of subjects for each category below will be provided by period and visit.

QTcF interval prolongation:

- QTcF interval < 450 ms for male or < 460 ms for female,
- QTcF interval \geq 450 ms for male or \geq 460 ms for female.

Change from baseline in QTcF interval:

- QTcF interval increases from baseline 30-60 ms,
- QTcF interval increases from baseline >60 ms.

A listing of subjects with ECG assessments, including the clinical evaluation results, will be provided.

13.7 Efficacy/PD Analyses

Efficacy analyses using laboratory parameters will be presented in both Conventional and SI units when applicable for the given parameter.

13.7.1 Primary Analyses

The primary efficacy endpoint is the cCa concentrations and 24-hour urinary calcium excretion after treatment with CLTX-305 for up to 24 weeks in Period 3.

cCa concentrations absolute values and change from baseline (Period 2 baseline) will be presented by visits and timepoints during Period 3. The mean ± SD cCa concentration at each visit and timepoint during Period 3 will be graphically represented. In addition, spaghetti plots of the cCa concentration will be provided by visits and timepoints during Period 3.

The 24-hour urinary calcium excretion (total) absolute values and change from baseline (Period 2 screening if available, otherwise Period 1 screening) will be summarized by visits during Period 3. In addition, the urinary calcium clearance (fractional) absolute values and change from baseline (Period 2 Day 1, 15 min pre-dose) will be tabulated by visits and time-intervals during Period 3. Finally, the mean ± SD urinary calcium clearance (total and fractional) and associated plots will also be presented by visits and time-intervals (where relevant) during Period 3.

The estimand for the primary efficacy analysis of cCa consists of the following attributes:

• Population: all subjects who received at least one dose of study drug in Period 3 (safety analysis set).

- Variable: the subject's cCa values at baseline (defined in section 10.1) and average of all Period 3, Week 24 values
- Intercurrent event: no strategy was constructed before all subjects completed Period 3, Week 24. There were no early discontinuations. There were no prohibited concomitant medications taken during Week 24. All data are therefore included in the analysis.
- Population level summary: difference in average cCa at baseline and Period 3, Week 24

The estimand for the primary efficacy analysis of 24-hour urinary calcium excretion consists of the following attributes:

- Population: all subjects who received at least one dose of study drug in Period 3 (safety analysis set).
- Variable: 24-hour urinary calcium excretion of the subject at baseline and Period 3, Week 24
- Intercurrent event: no strategy was constructed before all subjects completed Period 3, Week 24. There were no early discontinuations. There were no prohibited concomitant medications taken during Week 24. All data are therefore included in the analysis.
- Population level summary: difference in 24-hour urinary calcium excretion at baseline and Period 3, Week 24

13.7.2 Secondary Analyses

The secondary efficacy endpoints at each visit and timepoints are presented in Table 6.

For each parameter in Table 6, absolute levels and change from baseline (where applicable) will be tabulated by visits, dose (for period 1 only) and timepoints (where relevant) and for each period separately. In addition, the mean ± SD and individual profiles for the absolute levels for selected parameters will be graphically presented by period, visits and timepoints (where relevant).

		Summary		
Specimen	Parameter	Absolute Value	Change from Baseline	Plots
	cCa levels			
	iPTH levels			
Blood	1,25-(OH) ₂ Vitamin D levels			
	eGFR levels			
	Albumin levels			
	Magnesium levels			
	Phosphorus levels			
	Creatinine levels			
	CTx levels		Period 1 only	
	P1NP levels		Period 1 only	
Urine	Fractional urinary calcium excretion			

Table 6: Efficacy/PD Parameters

		Sur	nmary	
Specimen	Parameter	Absolute Value	Change from Baseline	Plots
	Total urinary calcium excretion			
	Fractional urinary excretion for Magnesium			
	Tubular reabsorption of phosphate			
	Total urinary excretion for Magnesium			
	Total urinary excretion for Phosphate			
	Total urinary excretion for Sodium			
	Total urinary excretion for Potassium			
	Total urinary excretion for Citrate			
	Time-intervals and 24-hours levels for cAMP*		$\sqrt{**}$	
	Time-intervals for creatinine and pH			
	24 hours creatinine levels			
	24 hours pH levels			

* Not collected during the LTE.

** For Period 1 only.

13.7.4 Post-hoc Inferential Analysis

For Period 2 and Period 3, a paired t-test to test whether the mean of baseline is equal to the mean of values at each visit will be carried out for the following parameters:

- cCa,
- iPTH,
- Blood Phosphorus,
- Blood Magnesium,
- Total Calcium Excretion.

If multiple samples are planned to be collected at a visit (serial sampling), average for that visit will be derived as follow.

- **Day 1**: average of the Day 1 post-dose samples and the 15 min pre-dose sample from Day 2;
- Day 2: average of the Day 2 post-dose samples and the 15 min pre-dose sample from Day 3;
- **Day 3**: average of the Day 3 post-dose samples and the 15 min pre-dose sample from Day 4;
- **Day 4**: average of the Day 4 post-dose samples and the 15 min pre-dose sample from Day 5;
- **Day 5**: average of the Day 5 post-morning and post-evening samples;
- Week 8: average of the Week 8 pre and post-dose samples;
- Week 16: average of the Week 16 pre and post-dose samples;
- Week 24: average of the Week 24 pre and post-dose samples.

13.8 PK Analyses

PK parameters will be determined for Period 1 and Period 2 on days where intensive sampling is performed; and on Period 3 Week 24 (am). See Protocol Section 1.3.1, and Table 15, Table 16, Table 17 and Table 18, for intensive sampling times for PK and laboratory parameters. PK parameters will not be calculated in those cases where non-intensive sampling was conducted (see Table 12, Table 13 and Table 14).

PK parameters to be determined after QD administration in Period 1, Days 1, 2 and 3 are: C_{max} , t_{max} , $t_{\frac{1}{2}}$, AUC_{0-t}, AUC₀₋₂₄, AUC_{0-inf}.

The steady state PK parameters (C_{max} , t_{max} , Trough concentration [C_{min}] and AUC_{0-tau}) will also be determined after BID administration in Period 1 Day 5, Period 2 Day 5 (i.e. when intensive sampling was conducted) and Period 3 Week 24 (after the am dose).

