## 1.3.1 Pharmacokinetic, Pharmacodynamic, and Urine Sampling Times

**Table E Non-intensive BID Sampling Days** 

Period 1: Day 4 (BID Dosing)
Period 3: PK/PD sampling days

	Timepoint ± 20 min. (relative to AM dose)
Blood Assays	
PK  samples	-15 min, +30 min, 2, 4, 8, 11, 13 hrs
Intact PTH	-15 min, +30 min*, 2, 4, 8, 11, 13, 17 hrs
Serum bone markers: CTX, P1NP	-15 min, 13 hrs
1, 25-(OH) 2 Vitamin D, cAMP	-15 min, 4, 8, 13,17, 24 hrs 
Ca, PO 4 , Mg, Cr, albumin	-15 min, +30 min*, 2, 4, 8, 11, 13, 17, 24 hrs
K, CK	-15 min, 13 hrs
Urine Assays:	
Timed Interval Urine Collections:	
Ca, Mg, PO 4 , Cr, cAMP, pH	-15 min 0-4 h, 4-8 h, 8-13 h, 13-17 h, 17-24 h
24-Hour urine: Ca, Mg, PO 4 , Cr, Na, K, Citrate, pH	0, 24 hrs (Start collection after first morning void and end 24 hours later)

PK in Period 3 only collected at 24 weeks;

Table F Non-intensive BID Sampling Days - (if CLTX-305 (encaleret) dose is  $\leq$  180 mg BID)

Period 2: Days 1, 2, 3 & 4

	Timepoint ± 20 min. (relative to AM dose)
Blood Assays	
PK samples	-15 min, 2, 4 hrs
Intact PTH	-15 min, +30 min, 2, 4, 8, 11, 13, 17 hrs
1, 25-(OH) 2 Vitamin D	-15 min, 4, 8, hrs
Ca, PO 4 , Mg, Cr, albumin	-15 min, +30 min, 2, 4, 8, 11, 13, 17 hrs
K, CK	-15 min, 13 hrs
Urine Assays:	
Timed Interval Urine Collections: Ca, Mg, PO 4 , Cr, pH	-15 min  , 0-4 h, 4-8 h, 8-13 h, 13-17 h, 17-24 h
24-Hour urine: Ca, Mg, PO 4 , Cr, Na, K, Citrate, pH	0, 24 hrs (Start collection after first morning void and end 24 hours later)

 min urine is done on Period 2 (Day 1) only

<sup>2 24 hour timepoint only collected in Period 3

\* +30 min timepoint only collected in Period 3 at 24 weeks

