## Table H Intensive Sampling Days for QD dosing

Period 1: Days 1, 2, 3

	Timepoint ± 10 min (relative to AM dose)	
Blood Assays:		
PK samples	-15 min, +30 min, 1, 1.5, 2, 3, 4, 6, 8, 13 hrs	
Intact PTH	-15 min, +30 min, 1, 1.5, 2, 3, 4, 6, 8, 13, 17 hrs	
Serum bone markers: CTX, P1NP	-15 min, 13 hrs	
1, 25-(OH) 2 Vitamin D, cAMP	-15 min, 4, 8, 13, 17 hrs	
Ca, PO 4 , Mg, Cr, albumin	-15 min, +30 min, 1, 2, 3, 4, 6, 8, 13, 17 hrs	
K, CK	-15 min, 13 hrs	
Urine Assays		
Timed Interval Urine Collections: Ca, Mg, PO 4 , Cr, cAMP, pH	-15 min  , 0-4 h, 4-8h, 8-13h, 13-17h, 17-24 h	
24-Hour urine: Ca, Mg, PO 4 , Cr, Citrate, Na, K, pH	0, 24 hrs (Start collection after first morning void and end 24 hours later)	

 min urine is done on Period 1 (Day 1) only

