#### 2.2.1 Pharmacokinetics and Product Metabolism

CLTX-305 (Nonproprietary name: encaleret, molecular formula  $(C_{29}H_{33}ClFNO_4)_2 \cdot H_2SO_4 \cdot H_2O$ , molecular weight 1144.15) is formulated as 5, 10, 30 and 60 mg white film coated tablets for the current clinical trial. The 10 and 30 mg dosage strengths are round tablet presentations; the 60 mg dosage strength can be round or a modified oval tablet presentation. The active agent inhibits the CaSR, via allosteric modulation, with an  $IC_{50}$  of 86.2 + 6.2 nM (in cell-based assays at 2 mM extracellular calcium). In humans, two major glucuronide metabolites (M1 and M3) occur. M1 ( $IC_{50} > 3000$  nM) is inactive and M3 ( $IC_{50}$  67.3 + 6.6 nM) is active.

CLTX-305 (encaleret) is rapidly absorbed in humans ( $t_{max}$  median 1.5 hr. (range 0.75–3 h at most single doses or at steady-state). The elimination half-life (t1/2) is approximately 11-14 hours at steady state (14 days). Dose-proportional increases in plasma CLTX-305 (encaleret) concentrations were documented over the dose range (5, 15, 30, 50 and 100 mg) in the fasted state without significant food effect. CLTX-305 (encaleret) showed minimal accumulation when administered once daily (QD) for two weeks in Japanese postmenopausal women. Based on non-clinical data, fecal excretion was the main route of elimination. In humans, excretion of unchanged CLTX-305 (encaleret) and metabolites into urine was minimal (< 5% as total of parent and metabolite).

The two major glucuronide metabolites showed similar pharmacokinetics as the parent drug, with M1 median tmax approximately 2 hr. and M3 median tmax approximately 1.5 hr. For M1 (inactive), concentrations in plasma were approximately 2-fold higher than those of parent

drug; M3 (active) concentrations were low (10% compared to parent). Neither M1 nor M3 showed prolonged elimination.

No significant age-related or race differences (US population vs. Japanese participants) were observed in CLTX-305 (encaleret) pharmacokinetics. AUC and Cmax values may be approximately 37% and 30% higher in females but these differences were not significant when body weight was taken into account. Hepatic and renal impairment studies have not been conducted.

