In Period 1, eligible Cohort 1 participants are admitted to the NIH CC after completing screening tests. On days 1-3 of admission, Cohort 1 participants will undergo single daily dosing and protocol-specified dose-escalation of CLTX-305 (encaleret) from the initial dose of 30 mg on Day 1, increasing to a maximum dose of 180 mg on Day 3. Based on the individualized responses to QD dose escalation an individualized dose of CLTX-305 (encaleret) will be chosen for BID administration on Days 4 and 5.

Days 1, 2 and 3 (QD Dose Escalations): Up to 8 participants (minimum of 5) will undergo a single-dose, dose-escalation over the first 3 days of admission in Period 1. Morning doses will be administered on Days 1, 2 and 3, respectively, accompanied by frequent blood and urine sampling for 24-hours for PK/PD measures. CLTX-305 (encaleret) will be administered in the morning within 30 minutes prior to breakfast. If dose escalation is limited due to tolerability or hypercalcemia, then the investigator, in consultation with the Sponsor, may choose to interrupt the pre-specified dose escalation (for example see Section 6.1.7 and Section 8.2.1). In this case, the investigator, in consultation with sponsor, may choose to repeat the last well-tolerated dose on Days 2 and 3, or titrate down as appropriate.

Dose-escalation will take place sequentially on Days 1, 2 and 3 without interim wash-out because prior extensive PK-PD data supports minimal drug accumulation over 24 hours when dosed once daily (for details see the Investigator's Brochure). Similarly, it is expected that iPTH levels will not remain elevated for 24 hours after dosing when CLTX-305 (encaleret) is administered once-daily. However, any carryover effects that may occur should not confound the objective of demonstrating an acutely efficacious dose of CLTX-305 (encaleret). For any given participant, cCa values > 10.5 mg/dL, during a dosing interval, will indicate that a top dose of CLTX-305 (encaleret) has been reached for that individual and further dose escalation will not be necessary. In this scenario, the investigator, in consultation with the Sponsor, may choose to repeat the last well-tolerated dose on the remaining QD testing days (e.g., Days 2 and 3), as appropriate. Detailed examples of dose and titration modifications based on the cCa response are shown in Figure E in Section 8.2.

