Outpatient testing done in Period 1 on day 7-8 (~ 24-48 hours after expected discharge from the NIH clinical center) will ideally be collected at the NIH CC. If this is not practical, with the participant's permission, contact information for the participant will be provided to a sponsor-contracted healthcare service to schedule a mutually agreeable time for sample collection in the home. Blood samples collected will be evaluated for CLTX-305 (encaleret) concentrations as well as for blood creatinine, albumin, calcium, magnesium, phosphate, and PTH. This will allow both an evaluation of calcium homeostasis as well as a final PK sample while CLTX-305 (encaleret) concentrations are washing-out after Period 1. Given that the half-life of CLTX-305 (encaleret) at steady state is ~ 10-14 hours, the PK sample will represent a timepoint between 40-70 hours after the last dose of CLTX-305 (encaleret) (administered in the evening of Day 5). A telephone contact will be conducted on day 9-11 or once the calcium results are available to be reviewed with investigative site staff.

In order to characterize both the pre-study calcemic status as well as changes associated with experimental interventions, the protocol will rely on frequent measurement of albumin-corrected blood calcium concentrations. Assays will be conducted according to specifications of the NIH Clinical Center Laboratory, Bethesda, MD. The main indicator of normal versus abnormal blood calcium levels will be based on the correction for serum or plasma albumin according to the formula corrected calcium (cCa) = measured total calcium (mg/dL) + 0.8(4 –albumin (g/dL)) OR measured total calcium (mmol/L) + 0.2(4 –albumin (g/dL)), recognizing that the total calcium reported in SI units (mmol/L) can be converted to conventional units (mg/dL) by multiplying by 4. Given that enrolled participants are expected to have both normal and stable albumin levels, the measures of total calcium and cCa are likely to be similar throughout the time course of this study. Ionized calcium assays will also be available at the NIH Clinical Center investigative site and can be measured either in the event of severe hypocalcemia or if there is any question about the accuracy of the cCa measure. Collection of ionized calcium will occur at the discretion of the expert investigators based on the clinical scenario on a case-by-case basis.

# 8.2.2 Period 2 (BID Dosing) - Cohorts 1 and 2

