13.8.3 Pharmacokinetics (PK) Data Analysis Methods

PK parameter estimates for CLTX-305 (encaleret) in plasma will be calculated by ICON using standard noncompartmental methods of analysis found in WinNonlin Phoenix version 8.1 or higher (Certara, Princeton, NJ, USA).

For calculation of AUC, BQL values on the leading edge of the profile (i.e., before t_{max}) are set equal to zero in the dataset loaded into WinNonlin (WNL) for PK analysis. BQL values after t_{max} are set to missing. BLQ values embedded between two measurable values will be treated as missing. Actual times will be used in the calculation of PK parameters. If actual times are missing, then nominal times will be used.

Descriptive statistics (n, mean, SD, %CV, median, minimum, maximum, geometric mean, and geometric CV) of PK parameters will be presented for each study dose, visit and period.

PK of CLTX-305 (encaleret) will be assessed by measuring the PK parameters included in Table 7.

Parameter	Description	PK Analysis Notes	SAS Programming Notes
C _{max}	Maximum plasma concentration. Observed peak analyte concentration obtained directly from the experimental data without interpolation, expressed in concentration units	single and multiple doses	Cmax from WNL
t _{max}	Time to reach Cmax in plasma. The time to reach maximum concentration is obtained directly from the experimental data without interpolation and expressed in time units.	single doses and multiple doses	Tmax from WNL

Table 7: PK Parameters

Parameter	Description	PK Analysis Notes	SAS Programming Notes
t _{1/2}	Terminal elimination phase half-life expressed in time units. $t_{1/2}$, will be calculated as ln2/Lambda z, where Lz is as defined below.	Single dose If there is no valid terminal phase and terminal elimination rate constant (Lambda z), t _{1/2} cannot be calculated	HL_Lambda_z from WNL Flag to List only if: AUC_%_obs >20% OR Rsq_< 0.8
Lambda z	First-order rate constant associated with the terminal (log-linear) portion of the curve. Estimated by linear regression of time vs. log concentration.	Single dose	Lambda_z from WNL Flag to list only
AUC _{0-t}	Area under the concentration-time curve from time 0 (dosing) to the time of the last quantifiable concentration AUC(0-T) is expressed in concentration*time units.	Single dose Calculated by the linear up/log down method in WNL.	AUClast from WNL

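### AUC0-inf on Period 1 Days 2 and 3 is reported as a single-dose value but contains residue from earlier doses, and the Day 7–8 washout sample feeds no PK parameter

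*SAP*

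**What the plan says.** - **Parameters.** SAP 13.8 states "PK parameters to be determined after QD administration in Period 1, Days 1, 2 and 3 are" Cmax, tmax, t½, AUC0-t, AUC0-24 and AUC0-inf. SAP Table 7 marks t½ and the three AUCs as single-dose parameters. SAP 13.0 summarises the AUCs and t½ as geometric means by dose level and study day.
- **Dosing.** Protocol 6.1.3: "Dose-escalation will take place sequentially on Days 1, 2 and 3 without interim wash-out". The reason given is minimal accumulation over 24 h, with no figure. The section adds that carry-over should not confound finding an acutely effective dose.
- **Sampling.** Protocol Table H lists PK times on Days 1–3 as "15 min, +30 min, 1, 1.5, 2, 3, 4, 6, 8, 13 hrs", the first being before the dose. Day 4 (Protocol Table E) also starts with a pre-dose sample: "15 min, +30 min, 2, 4, 8, 11, 13 hrs". Each once-daily dose therefore has a sample about 23.75 h later. SAP 10.3 uses the next-day pre-dose result for fractional excretion; no such rule is written for PK.
- **Flag.** For both t½ and AUC0-inf, SAP Table 7 has "Flag to List only if: AUC_%_obs >20% OR Rsq_< 0.8".
- **Half-life.** Protocol 2.2.1: "The elimination half-life (t1/2) is approximately 11-14 hours at steady state (14 days". Protocol 8.2.1 gives about 10–14 h.
- **Late sample.** Protocol 8.2.1 describes the Day 7–8 draw as "a final PK sample while CLTX-305 (encaleret) concentrations are washing-out after Period 1", 40–70 h after the Day 5 evening dose. After Day 5 dosing, SAP 13.8 derives only Cmax, tmax, trough and AUC0-tau.

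**The concern.** On Days 2 and 3 the measured curve is the sum of that day's dose and whatever remains of earlier doses. Extending it to infinity credits all of that residue to the current dose. The size of the error depends on the dose path, which is individualised, so AUC0-inf at different doses and days is inflated by different amounts, in at most 8 participants and with nothing in the table to show it.

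Two further gaps sit beside this. The SAP does not say which sample ends each once-daily profile, and that decides how many t½ and AUC0-inf values survive the 20% flag. The one sample drawn well into washout is used in no parameter.

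**Working it through.** **Check of the plan's own figure.** SAP 8.0 sets the dosing intervals at 9 h and 15 h. Day 7 at the morning-dose time is 15 + 24 = 39 h after the Day 5 evening dose. Day 8 at the evening-dose time is 39 + 24 + 9 = 72 h. This agrees with the stated 40–70 h. The documents give no expected carry-over or extrapolated share to reproduce.

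**1. Carry-over in AUC0-inf.** Assume linear one-compartment kinetics. The fraction of a dose's area still to come after 24 h is r = 2^(−24/t½): 0.220 at 11 h and 0.305 at 14 h. Excess relative to the true single-dose value:
- Day 2 = D1·r / D2
- Day 3 = (D2·r + D1·r²) / D3

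| Path (mg) | Day | 11 h | 14 h |
|---|---|---|---|
| 30-90-180 | 2 | 30 × 0.220 / 90 = 7.3% | 10.2% |
| 30-90-180 | 3 | (90 × 0.220 + 30 × 0.0486) / 180 = 11.8% | 16.8% |
| dose repeated | 2 | 22.0% | 30.5% |
| 30 then 10 | 2 | 3 × 0.220 = 66% | 91% |

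The paths come from Protocol Figure E, and Protocol 6.1.3 allows a dose to be repeated.

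**2. Extrapolated share.** I read the flag variable as the extrapolated percentage, which SAP Table 7 elsewhere calls AUC%Extrap. With the next-day pre-dose sample as the last point, the share is 2^(−23.75/t½):
- 10 h: 19.3%
- 11 h: 22.4%
- 14 h: 30.9%

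The break-even half-life is 23.75 × ln 2 / ln 5 = 10.2 h. Allowing for absorption (tmax "median 1.5 hr. (range 0.75–3 h at most single doses or at steady-state", share multiplied by ka/(ka − k)) moves these to 19.8%, 23.0% and 31.4%. If half-lives are log-normal with geometric mean 11–14 h and an assumed between-subject CV of 20–40%, the chance of exceeding 10.2 h is 58–94%.

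**3. If accumulation really is minimal.** By superposition, the share of area after 24 h is 1 − 1/Racc, so 20% corresponds to Racc = 1.25 (marginally lower at 23.75 h). One-compartment kinetics at 11–14 h imply Racc = 1/(1 − r) = 1.28–1.44. With two-phase kinetics and Racc = 1.10:
- the share at 23.75 h is 9.2%, which passes;
- Day 2 carry-over for 30 then 90 mg is (1 − 1/1.10) × 30/90 = 3.0%.

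**4. What the Day 7–8 sample could add.** The fraction remaining, 2^(−t/t½), is 8.0–13.8% at 40 h and 1.2–3.1% at 70 h for 11–14 h. Extrapolation after the Day 5 evening dose would be well under 20%.

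**5. Form of a correction.** Residue at the pre-dose concentration Cpre contributes Cpre/λz to AUC0-inf. Over 24 h it contributes Cpre(1 − r)/λz, which is 0.780/0.0630 = 12.4·Cpre at 11 h and 0.695/0.0495 = 14.0·Cpre at 14 h. Subtracting a constant Cpre removes 24·Cpre, which is 1.7–1.9 times too much.

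**The case against.** The case for leaving the plan alone is substantial in places.

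- **Failure of the flag is not established.** A reader might infer that most t½ and AUC0-inf values will be list-only. That needs one-compartment kinetics and a half-life above 10.2 h. The 11–14 h figure is for steady state, no single-dose half-life is given, the protocol's other figure starts at 10 h, and its claim of minimal accumulation points the other way. This stands.
- **Stopping at 13 h is not the natural reading.** If the profile ended there, the share would be 44–53%. But SAP Table 7 defines AUC0-24 from observed data, which needs the next-day pre-dose sample. What remains is a wording gap.
- **Half-life is not biased by carry-over.** A reader might extend the bias to t½. Under linear kinetics residue declines at the same terminal rate, so the slope is unaffected.
- **No dose-proportionality analysis is planned.** PK is descriptive. The harm is to summaries by dose and day.
- **The late sample's purpose is not stated as half-life.** The protocol mentions washout and the half-life but names neither t½ nor AUC0-inf as the aim. The sample can still enter the concentration summaries in SAP 13.8.2.
- **The largest figures are for an unlikely path.** Going from 30 to 10 mg needs corrected calcium above 10.5 mg/dL after a dose that the protocol expects to be ineffective or minimally effective.
- **The protocol accepts carry-over.** It does so for finding an acutely effective dose. That does not make Days 2 and 3 single-dose profiles for AUC0-inf.

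None of this answers the central point. Values that pass the 20% flag can still carry residue, and nothing in the SAP marks or removes it.

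**Conclusion.** The point holds for AUC0-inf on Days 2 and 3, which is inflated by design. With linear one-compartment kinetics and a half-life of 11–14 h, the excess is about 7–10% on Day 2 and 12–17% on Day 3 for 30-90-180 mg. It is 22–31% for a dose repeated on Day 2, and 66–91% for 30 then 10 mg. If the accumulation ratio is 1.10, it falls to about 3% on Day 2 for 30 then 90 mg. The direction does not depend on the model; the size does.

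Loss of t½ and AUC0-inf to the list-only rule is a risk that depends on kinetics the documents do not settle. The Day 7–8 sample feeds no PK parameter, which is a missed use of data and not a breach of a stated purpose. These are secondary, descriptive endpoints, so the matter is worth correcting but does not touch the primary results.

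**What to change.** In SAP 13.8 and Table 7:

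1. State that the next-day pre-dose sample closes each once-daily profile on Days 1–3.
2. Report AUC0-inf as a single-dose parameter for Day 1 only. Alternatively, on Days 2–3 subtract the decaying residual, Cpre/λz, and not a constant concentration. Label any uncorrected Day 2–3 AUC as including carry-over.
3. Add a terminal half-life after the Period 1 Day 5 evening dose, from the later post-dose samples plus the Day 7–8 sample when quantifiable, labelled as following repeated dosing.

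Use one name for the extrapolated percentage in the flag and in its own row of Table 7.

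**Cost.** SAP wording and PK programming only; every sample is already in the schedule. SAP 4.0 allows updates before database lock and otherwise requires unplanned analyses to be documented in the CSR.

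**Limits.** Restricting to Day 1 leaves single-dose AUC0-inf at 30 mg only, and those values may still exceed 20% extrapolation. The residual correction relies on that day's λz. The added half-life depends on one late sample: if it is below quantification, SAP 13.8.3 sets it to missing. It supplements the single-dose endpoint and does not replace it.
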